## 10.5. Liver Safety: Required Actions and Follow-up Assessments

Phase 2 liver chemistry stopping criteria are designed to assure subject safety and to evaluate liver event etiology. The guidelines provided below are based on the European Association for the Study of the Liver Clinical Practice Guidelines: Drug-induced Liver Injury (2019) and Food and Drug Administration 2009 Guidance for Industry Drug-induced Liver Injury: Premarketing Clinical Evaluation.

### Phase 2 Liver Chemistry Stopping Criteria and Follow-up Assessments

Liver Chemistry Stopping Criteria	
ALT or AST-absolute	ALT or AST $\geq 5 \times$ ULN
ALT or AST Increase	ALT or AST $\geq 3 \times$ ULN persists for $\geq 4$ weeks
Bilirubina,b	ALT or AST $\geq 3 \times$ ULN and total bilirubin $\geq 2 \times$ ULN ( $> 35\%$ direct bilirubin)
International Normalized Ratio (INR)b	ALT or AST $\geq 3 \times$ ULN and INR $> 1.5$
Cannot Monitor	ALT or AST $\geq 3 \times$ ULN and cannot be monitored twice weekly for 4 weeks
Symptomaticc	ALT or AST $\geq 3 \times$ ULN associated with symptoms (new or worsening) believed to be related to liver injury or hypersensitivity
Suggested Actions, Monitoring, and Follow-up Assessments	
Actions	

 
• Immediately discontinue study drug.
 
• Report the event to the sponsor/designee within 24 hours.
 
• Complete an SAE eCRF if the event met the criteria for an SAE.b
 
• Perform follow-up assessments as described in the Follow-up Assessment column.
 
• Monitor the subject until liver chemistry test abnormalities resolve, stabilize, or return to baseline.
 
	
 
• Viral hepatitis serology.c
 
• Obtain blood samples for PK analysis after the most recent dose.d
 
• Obtain serum creatine phosphokinase, lactate dehydrogenase, gamma glutamyl transferase, glutamate dehydrogenase, and serum albumin.
 
• Fractionate bilirubin if total bilirubin <math>\geq 2 \times</math> ULN.
 
• Obtain complete blood count with differential to assess eosinophilia.
 


MONITORING:
 
If ALT or AST <math>\geq 3 \times</math> ULN AND total bilirubin <math>\geq 2 \times</math> ULN or INR <math>> 1.5</math>:
 
 
Repeat liver chemistry tests (include ALT, AST, alkaline phosphatase, total bilirubin, and INR) and perform liver event follow-up assessments within 24 hours.
 
Monitor subject twice weekly until liver chemistry test abnormalities resolve, stabilize, or return to baseline.
 
A hepatology consultation is recommended.
 
 
If ALT or AST <math>\geq 3 \times</math> ULN AND total bilirubin <math>< 2 \times</math> ULN and INR <math>\leq 1.5</math>:
 
 
Repeat liver chemistry tests (include ALT, AST, alkaline phosphatase, total bilirubin, and INR) and perform liver chemistry follow-up assessments within 24 to 72 hours.
 
Monitor subjects twice weekly until liver chemistry abnormalities resolve, stabilize, or return to baseline, or the study drug has been discontinued; then decrease monitoring to once weekly or less.
 
Do not restart/rechallenge subject with study drug unless allowed per-protocol and sponsor approval is granted.
 
	
 
Record the appearance or worsening of clinical symptoms of liver injury, or hypersensitivity, on the eCRF.
 
Record use of concomitant medications (including acetaminophen, herbal remedies, and other over-the-counter medications) on the concomitant medications eCRF.
 
Record alcohol use on the liver event alcohol intake form.
 
 
If ALT or AST <math>\geq 3 \times</math> ULN AND total bilirubin <math>\geq 2 \times</math> ULN or INR <math>> 1.5</math> obtain the following in addition to the assessments listed above:
 
 
Antinuclear antibody, anti-smooth muscle antibody, type 1 anti-liver kidney microsomal antibodies, and quantitative total immunoglobulin G or gamma globulins.
 
Serum acetaminophen adduct assay, when available, to assess potential acetaminophen contribution to liver injury in subjects with definite or likely acetaminophen use in the preceding week.
 
Liver imaging (ultrasound, magnetic resonance, or computerized tomography) to evaluate liver disease.
 
Liver biopsy may be considered and discussed with local specialist if available, for instance: 
 
In subjects when serology raises the possibility of autoimmune hepatitis.
 
In subjects when suspected drug-induced liver injury progresses or fails to resolve on withdrawal of study drug.
 
 
 

---	---

	

○ In subjects with acute or chronic atypical presentation.

● If liver biopsy conducted provides biopsy information.

--	---

Abbreviation: ALT = alanine transaminase; AST = aspartate transaminase; eCRF = electronic case report form; PK = pharmacokinetic; SAE = serious adverse event; ULN = upper limit of normal.

a Serum bilirubin fractionation should be performed if testing is available. If serum bilirubin fractionation testing is unavailable, **record the absence/presence of detectable urinary bilirubin on dipstick** which is indicative of direct bilirubin elevations suggesting liver injury.

b All events of ALT or AST  $\geq 3 \times$  ULN **and** total bilirubin  $\geq 2 \times$  ULN ( $> 35\%$  direct bilirubin) or ALT or AST  $\geq 3 \times$  ULN **and** INR  $> 1.5$  may indicate severe liver injury (**possible “Hy’s Law”**) **and must be reported to sponsor in an expedited manner and as an SAE.** The INR stated threshold value will not apply to subjects receiving anticoagulants.

c New or worsening symptoms believed to be related to liver injury (such as fatigue, nausea, vomiting, right upper quadrant pain or tenderness, or jaundice) or hypersensitivity (such as fever, rash, or eosinophilia).

d Record the date/time of the PK blood sample draw and the date/time of the last dose of study drug prior to the blood sample draw on the eCRF. If the date/time of the last dose is unclear, provide the subject’s best approximation. If the date/time of the last dose cannot be approximated OR a PK sample cannot be collected in the time period indicated above, do not obtain a PK sample. Instructions for sample handling and shipping are in the Study Laboratory Manual.

## 10.6. Abbreviations and Definitions

Abbreviation	Definition
ADA	anti-drug antibody
ADL	activities of daily living
AE	adverse event
AN	abscess and inflammatory nodule
AUC	area under the concentration-time curve
AUC 0-∞	area under the plasma concentration-time curve extrapolated to infinity
AUC 0-τ	area under the plasma concentration-time curve over a dosing interval
BID	twice daily
CFR	Code of Federal Regulations
CI	confidence interval
C max	maximum observed plasma concentration
COVID-19	coronavirus disease of 2019
CRF	case report form
CRO	Contract Research Organization
C-SSRS	Columbia-Suicide Severity Rating Scale
CTCAE	Common Terminology Criteria for Adverse Events
CV%	percent coefficient of variation
DLQI	Dermatology Life Quality Index
DMC	data monitoring committee
DNA	deoxyribonucleic acid
ECG	electrocardiogram
eCRF	electronic case report form
EQ-5D	European Quality of Life-5 Dimensions
EudraCT	European Union Drug Regulating Authorities Clinical Trials
FAS	Full Analysis Set
FSH	follicle-stimulating hormone
GCP	Good Clinical Practice
HADS	Hospital Anxiety and Depression Scale
HiSCR50	hidradenitis suppurativa clinical response 50 is defined as at least a 50% reduction from baseline in the total abscess and inflammatory nodule count, with no increase from baseline in abscess or draining fistula count
HiSCR75	HiSCR75 defined as at least a 75% reduction from baseline in the total abscess and inflammatory nodule count, with no increase from baseline in abscess or draining fistula count
HiSCR90	HiSCR90 defined as at least a 90% reduction from baseline in the total abscess and inflammatory nodule count, with no increase from baseline in abscess or draining fistula count
HiSCR100	HiSCR100 defined as a 100% reduction from baseline in the total abscess and inflammatory nodule count, with no increase from baseline in abscess or draining fistula count
HiSQOL	Hidradenitis Suppurativa Quality of Life
HIV	human immunodeficiency virus
HRT	hormonal replacement therapy
HS	hidradenitis suppurativa
HS-PGA	Hidradenitis Suppurativa-Physician's Global Assessment
IBD	inflammatory bowel disease
ICE	intercurrent event
ICH	International Council for Harmonisation

Abbreviation	Definition
ICF	informed consent form
IGRA	interferon-gamma release assay
IEC	Independent Ethics Committee
IHS4	International Hidradenitis Suppurativa Severity Score System
IL	interleukin
IL-17A	Interleukin-17A
IMP	investigational medicinal product
IRB	Institutional Review Board
ISR	injection site reaction
IV	intravenous(ly)
IXRS	Interactive Voice/Web Response System
JAK	Janus-kinase
MMRM	nonlinear mixed effects model with repeated measures
NOAEL	no observed adverse effect level
NRS	numeric rating scale
PASI	Psoriasis Area and Severity Index
PASI90	Psoriasis Area and Severity Index response of 90%
PGIC	Patient Global Impression of Change
PK	pharmacokinetic(s)
PsA	psoriatic arthritis
QW	every week
Q2W	every other week
SAE	serious adverse event
SARS-CoV-2	severe acute respiratory syndrome coronavirus
SC	subcutaneous(ly)
SF-12v2	Short Form-12v2™ Health Survey
SoA	Schedule of Activities
SUSAR	suspected unexpected serious adverse reaction
$t_{\frac{1}{2}}$	half-life
TB	tuberculosis
TEAE	treatment-emergent adverse events
Th17	T-helper 17 cell
$t_{\max}$	time to maximum observed concentration
TNF- $\alpha$	tumor necrosis factor- $\alpha$
US	United States
USPI	United States prescribing information
WOCBP	women of childbearing potential

1. LIST OF ABBREVIATIONS

Abbreviation or Term	Definition
ADA	anti-drug antibody
AESI	adverse event of special interest
ALP	Alkaline Phosphatase
ALT	Alanine Transaminase
AN	abscess and inflammatory nodule
AR	autoregressive
AST	Aspartate Transferase
ATC	Anatomical Therapeutic Chemical
BLQ	below limit of quantification
BMI	body mass index
bpm	beats per minute
C	Celsius
CI	confidence interval
cm	centimeters
CRO	clinical research organization
CSR	clinical study report
CS	compound-symmetric
C-SSRS	Columbia-suicide severity rating scale
CV	coefficient of variation
DBP	diastolic blood pressure
DILI	drug-induced liver injury
DLQI	Dermatology Life Quality Index
ECG	electrocardiogram
EQ-5D	European Quality of Life-5 Dimensions
FAS	full analysis set
FASP2	full analysis set period 2
HADS	Hospital Anxiety and Depression Scale
HiSCR	Hidradenitis suppurative clinical response
HiSCR100	Hidradenitis Suppurativa Clinical Response 100
HiSCR50	Hidradenitis Suppurativa Clinical Response 50
HiSCR75	Hidradenitis Suppurativa Clinical Response 75
HiSCR90	Hidradenitis Suppurativa Clinical Response 90
HiSQOL	Hidradenitis Suppurativa Quality of Life
HS-PGA	Hidradenitis Suppurativa-Physician's Global Assessment
ICF	informed consent form
IDMC	independent data monitoring committee
IHS4	International Hidradenitis Suppurativa Severity Score System
IL	interleukin
INR	international normalized ratio
ISR	injection site reaction
IXRS	Interactive Voice/Web Response System
JAK	Janus Kinase
kg	kilograms
LFT	liver function test
LS	least square
MACE	Major adverse cardiovascular and cerebrovascular event
MCMC	Markov Chain Monte Carlo
MedDRA	Medical Dictionary for Regulatory Activities

Abbreviation or Term	Definition
mmHg	millimeters of mercury
MMRM	mixed model repeated measures
NRI	non-response imputation
NRS	numeric rating scale
PGIC	Patient Global Impression of Change
PK	pharmacokinetic
PRO	patient reported outcome
PT	preferred term
QW	every week
SAE	serious adverse event
SAF	safety analysis set
SAFP2	safety analysis set period 2
SAP	statistical analysis plan
SBP	systolic blood pressure
SD	standard deviation
SF-12	Short Form-12v2™ Health Survey
SoA	schedule of activities
SOC	system organ class
TEAE	treatment-emergent adverse event
TNFi	tumor necrosis factor-alpha inhibitor
ULN	upper limit of normal
UN	unstructured
WHODD	World Health Organization Drug Dictionary

2. INTRODUCTION

This study will be conducted to evaluate the efficacy and safety of izokibep in the treatment of subjects with moderate to severe Hidradenitis Suppurativa (HS). Izokibep is a small protein molecule that acts as a selective, potent inhibitor of Interleukin (IL) 17A, to which it binds with high affinity.

This study investigates izokibep in subjects with active HS, including tumor necrosis factor-alpha inhibitor (TNFi) naïve subjects, and those who had an inadequate response or intolerance to TNFi, or for whom TNFi is contraindicated. The study is intended to be 1 of 2 adequate and well-controlled studies to support a claim of efficacy of izokibep in subjects with HS. Hidradenitis suppurativa clinical response 75 (HiSCR75) at Week 12 will be utilized to compare izokibep to placebo, for the primary endpoint.

This statistical analysis plan (SAP) will define the final analyses planned for the study.

The study will be terminated early after all subjects completed (or discontinued) treatment at Week 32. A decision was made to write an abbreviated clinical study report (CSR). The analyses described thereafter reflect this decision.

3. STUDY OBJECTIVES

3.1 Primary Objective

The primary objective of this study is:

- To demonstrate the efficacy of izokibep compared with placebo, as measured by percentage of subjects achieving HiSCR75 at Week 12

3.2 Secondary Objectives

Secondary objectives of this study are:

- To demonstrate that izokibep is efficacious compared with placebo as measured by:
 - Percentage of subjects achieving HiSCR90 at Week 12
 - Percentage of subjects achieving HiSCR100 at Week 12
 - Percentage of subjects achieving HiSCR50 at Week 12
 - Percentage of subjects who experience ≥ 1 disease flare through 12 weeks of treatment
 - Change in Dermatology Life Quality Index (DLQI)
 - Percentage of subjects with baseline Hurley Stage II who achieve abscess and inflammatory nodule (AN) count of 0, 1, or 2 at Week 12
 - Percentage of subjects achieving at least 3-point reduction from baseline in Numeric Rating Scale (NRS) Patient Global Assessment of Skin Pain at its worst among subjects with baseline NRS ≥ 4
- To assess the safety and tolerability of izokibep as measured by the incidence of treatment-emergent adverse events (TEAEs), events of interest, serious adverse events (SAEs), and clinically significant laboratory values and vital signs

3.3 Exploratory Objectives

Exploratory objectives of this study are:

- To demonstrate that izokibep is efficacious compared with placebo at timepoints through Week 16 and to estimate izokibep efficacy at timepoints after Week 16, as measured by:
 - Percentage of subjects who achieve HiSCR75 at Weeks 2, 4, 8, 16, 32, and 52
 - Percentage of subjects who achieve HiSCR90 at Weeks 2, 4, 8, 16, 32, and 52
 - Percentage of subjects who achieve HiSCR100 at Weeks 2, 4, 8, 16, 32, and 52
 - Percentage of subjects who achieve HiSCR50 at Weeks 2, 4, 8, 16, 32, and 52
 - Percentage of subjects with baseline Hurley Stage II who achieve AN count of 0, 1, or 2 at Weeks 4, 8, 16, 24, 32, and 52
 - Percentage of subjects achieving at least 3-point reduction from baseline in NRS Patient Global Assessment of Skin Pain at its worst among subjects with baseline NRS ≥ 4
 - Mean change from baseline in NRS Patient Global Assessment of Skin Pain at its worst (all subjects)
 - Mean change from baseline in NRS Patient Global Assessment of Skin Pain on average (all subjects)
 - Modified Sartorius Score after 4, 8, 12, 16, 24, 32, and 52 weeks of treatment
 - HS flare, rates through 4 and 52 weeks of treatment
 - International Hidradenitis Suppurativa Severity Score System (IHS4) after 4, 8, 12, 16, 24, 32, and 52 weeks of treatment
 - Hidradenitis Suppurativa-Physician's Global Assessment (HS-PGA)
 - Mean change from baseline in draining tunnel count
- To explore the effect of izokibep on Patient Reported Outcomes (PROs) as measured by change from baseline over time in:
 - European Quality of Life-5 Dimensions (EQ-5D)
 - Hidradenitis Suppurativa Quality of Life (HiSQL)

- Hospital Anxiety and Depression Scale (HADS)
- Patient Global Impression of Change (PGIC)
- DLQI
- Short Form-12v2™ Health Survey (SF 12v2)
- To estimate the mean trough plasma level izokibep in subjects with HS
- To assess the immunogenicity of izokibep as measured by the presence of anti-drug-antibodies (ADAs)
- To assess biomarkers of anti-IL-17A treatment and biomarkers associated with HS efficacy (United States Only)

4. STUDY DESIGN

4.1 General Design

This is a Phase 3, pivotal, confirmatory, 1:1 randomized, double-blind, placebo-controlled, parallel group study to evaluate the efficacy and safety of izokibep in subjects with moderate to severe HS. Subjects must have HS lesions present in ≥ 2 distinct anatomic areas, 1 of which must be Hurley Stage II or Hurley Stage III, and a total AN count (total sum of abscesses and inflammatory nodules) of ≥ 5 . Subjects with draining fistula count of > 20 at screening or Day 1 will be excluded.

Overall, 250 subjects (125 subjects per treatment group) with moderate to severe HS are planned to be enrolled at sites globally in North America, Europe, and Asia Pacific. Additional sites and regions may be added.

Subjects meeting eligibility criteria will be randomized into 1 of 2 treatment groups in a 1:1 ratio as follows:

- Group 1 (n = 125): placebo every week (QW) from Day 1 through Week 15, then izokibep 160 mg QW from Weeks 16 to 51.
- Group 2 (n = 125): izokibep 160 mg QW from Day 1 through Week 51.

[figure not shown]
The first dose of study drug (i.e., izokibep or placebo) will be administered on Day 1.

Randomization will be stratified by prior TNFi use for HS (Yes/No) and Hurley Stage (II or III). Subjects enrolled with stable concomitant antibiotic use (dosing regimen has been stable for ≥ 4 weeks prior to first dose of study drug) will be capped at approximately 30%.

The maximum planned length of participation in the study for an individual subject is up to 63 weeks, which includes the following:

- Screening Period of up to 28 days (4 weeks)
- Treatment Period of 51 weeks
- Follow-up visit at 8 weeks after the last dose of study drug.

Figure 1: Study Design Schema

EOS = end of study; EOT = end of treatment; QW = every week

^aRandomization will be stratified by any prior TNFi use for hidradenitis suppurativa (Yes/No) and Hurley Stage (II or III).

^bSubjects in Group 1 (placebo QW) will receive placebo QW until Week 15, then izokibep QW beginning at Week 16 until Week 51. Subjects in Group 2 (izokibep QW) will receive izokibep QW.

^cAn 'end of treatment visit' will be conducted at Week 52 (± 5 days). A 'safety follow-up visit' will be conducted at Week 59 (± 5 days). For subjects who early terminate, the end of treatment visit should be completed 1 week after the last dose of study drug and safety follow-up visit completed 8 weeks after the last dose of study drug (± 5 days), where possible.

The primary analysis of primary and secondary endpoints will be conducted after all subjects have the opportunity to complete Week 12 assessments or early terminate from the study (all subjects complete week 12, or complete an assessment after week 12, or permanently discontinue from the study).

A separate, final, analysis of data will occur after all subjects have completed or discontinued from the study. This document defines the final analysis.

The study will be terminated early after all subjects completed (or discontinued) treatment at Week 32. A decision was made to write an abbreviated clinical study report (CSR). The analyses described thereafter reflect this decision.

4.2 Randomization and Treatment Assignments

Subjects will be randomized to the study drug or placebo (in a 1:1 ratio) on Day 1 by the Interactive Voice/Web Response System (IXRS).

Randomization will be stratified by prior TNFi use for HS (Yes/No) and Hurley Stage (II or III). Subjects on a stable dose of antibiotic will be capped at a rate of approximately 30%. Izokibep and matching placebo will be visually indistinguishable to prevent unblinding during preparation or administration of study treatment.

4.3 Blinding/Unblinding

The subject, site personnel, and sponsor/Contract Research Organization (CRO) study personnel and designees will be blinded to the randomization treatment group assignment (ie, izokibep or placebo). A subject's treatment assignment should be unblinded only when knowledge of the treatment is essential for the further management of the subject in this study. Unblinding at the site for any other reason will be considered a protocol deviation. The investigator should contact the medical monitor before unblinding any subject's treatment assignment, whenever possible. If an urgent therapeutic intervention

is necessary that warrants unblinding prior to contacting the medical monitor, the investigator can directly access the IXRS, or call the 24-hour emergency medical coverage line to unblind without medical monitor notification or agreement but must contact the medical monitor within 1 working day after the unblinding event.

If an SAE requires an expedited regulatory report to be sent to 1 or more regulatory agencies, sponsor/designee's safety staff may unblind the treatment assignment for the subject. A copy of the report, identifying the subject's treatment assignment, may be sent to that regulatory agency in accordance with local regulations.

4.4 Sample Size Considerations

In prior studies, HiSCR75 response rates among placebo recipients after 12 to 16 weeks of treatment have been approximately 10% to 20%. At Week 12 in this study, HiSCR75 response rates are expected to be 15% for placebo recipients and 35% for izokibep recipients. With 125 subjects receiving each treatment, this study will have approximately 95% power to demonstrate a difference in HiSCR75 response rates between arms. This calculation uses an unstratified test, with $\alpha = 0.05$, 2-sided.

5. CHANGES IN THE ANALYSES SPECIFIED IN THE PROTOCOL

The secondary endpoint, "Percentage of subjects who experience ≥ 1 disease flare through 12 weeks of treatment" has been moved down the hierarchy of secondary endpoint testing to be the (last) seventh one in the order of testing.

The exploratory endpoint "Change of Modified Sartorius Score from baseline, Weeks 4, 8, 12, and 16" will not be analyzed due to inconsistent and unreliable data collection.

Due to the early termination of the study and the decision to write an abbreviated clinical study report, exploratory efficacy analyses will not be performed as written in the protocol. The efficacy endpoints for which analyses will be done as-written will be limited to the following:

- Primary:
 - HiSCR75 at Week 16
- Secondary/Exploratory:
 - HiSCR90 at Weeks 2, 4, 8, 16, and 32
 - HiSCR100 at Weeks 2, 4, 8, 16, and 32
 - HiSCR50 at Weeks 2, 4, 8, 16, and 32
 - AN count of 0, 1, or 2 at Weeks 4, 8, 16, 24, and 32
 - Change in NRS Patient Global Assessment of Skin Pain at its worst in subjects with baseline NRS ≥ 4 at Weeks 4, 8, 16, 24, and 32
 - HS flares through Weeks 4, 16 and 52
 - Change from baseline to Weeks 4, 8, 16, and 24 in DLQI

All remaining exploratory efficacy endpoint analyses will not be performed.

Limited safety summaries are planned for the purposes of abbreviated CSR. Clinical laboratory data, ECGs, vital signs, and physical exam results will not be summarized. These data will be provided as datasets.

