8.6 Multiple Comparisons/Multiplicity

Hypotheses tested will be adjusted to control the familywise error rate in the strong sense at $\alpha = 0.050$, 2-sided. An adjustment of 0.0001 will be made to account for the unblinded data summaries reviewed by the DMC. The hypotheses will therefore be tested at $\alpha = 0.0499$.

The statistical comparisons for the primary efficacy endpoint and the secondary endpoints, all at Week 12, will be carried out in sequential order. The primary endpoint, comparing izokibep to placebo, will be tested first, with significance concluded if $p < 0.0499$. Testing of secondary endpoints will only be carried out if all prior tests, including the test of the primary endpoint, first show significance with $p < 0.0499$. If all prior tests are significant, testing will proceed in the following order:

- The first secondary endpoint: proportion of subjects achieving HiSCR90 at Week 12.
- The second secondary endpoint: proportion of subjects achieving HiSCR100 at Week 12.
- The third secondary endpoint: proportion of subjects achieving HiSCR50 at Week 12.
- The fourth secondary endpoint: change in DLQI from baseline to Week 12.
- The fifth secondary endpoint: achieving AN count of 0, 1, or 2 at Week 12 among subjects with baseline Hurley Stage II.
- The sixth secondary endpoint: proportion of subjects who achieve a reduction in pain NRS of at least 3 points from baseline to Week 12, among subjects with a pain NRS score of at least 4 at baseline.
- The seventh secondary endpoint: proportion of subjects who experience flares through Week 12.

If a null hypothesis is not rejected, p-values for subsequent hypotheses in the sequence will be reported as nominal and will not be used to assess objectives or make determinations of efficacy.

At the time of the primary analysis of Week 12 data, some data was available for subjects at Week 16, but not all. A cutoff date was chosen and subjects randomized before that cutoff date were included in summaries and analyses of Week 16 data; subjects randomized after that cutoff date were excluded from summaries and analyses of Week 16 data. When all subjects have completed or discontinued the terminated study at Week 32, a final analysis will be reported, which will include Week 16 data. Since Week 16 data will not be used for any alpha-preserving analyses, there will be no multiplicity adjustment for analyzing Week 16 data twice.

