9.5 Analysis of Primary Efficacy Endpoint

The primary efficacy variable is defined as HiSCR75 at Week 12.

The statistical null and alternative hypotheses to be used to assess the primary objective are:

$$H_0: \pi_{ABY} - \pi_{PBO} = 0$$

$$H_A: \pi_{ABY} - \pi_{PBO} \neq 0$$

where π_{ABY} and π_{PBO} are the proportion of subjects achieving HiSCR75 at Week 12 among subjects randomly assigned to receive izokibep and placebo, respectively.

The treatment policy strategy approach for the estimand will be used in general, so subjects will be included using observed data at Week 12 regardless of treatment compliance, use of rescue medications or procedures except as noted below, or any other protocol deviations.

Subjects who receive antibiotic therapy that could affect HS will be included in the primary analysis by imputing as non-responders (non-response imputation or NRI) at subsequent timepoints. A list of all oral antibiotic therapy that results in such imputation will be finalized after review of all oral antibiotic therapy received by any subject and before unblinding of the study, and will include tetracycline, clindamycin, and possibly other products. Similarly, subjects with missing HiSCR75 assessments at Week 12 due to discontinuing treatment due to an AE or lack of efficacy will also be imputed as NRI. These subjects will be identified by meeting any of the following criteria:

- Subject has adverse event with action taken = “Drug Withdrawn” and corresponding AE start date is before study day 84 and last dose of study drug is taken before study day 84 or
- Subject has last dose of study drug taken before study day 84 and reason for discontinuation of treatment is any of the following:
 - Adverse event
 - Death
 - Lack of efficacy
 - Disease progression

Other subjects with missing data will have efficacy data imputed using multiple imputation, as follows:

Multiple imputation will be implemented to replace missing endpoint data using multiple draws from a posterior predictive distribution estimated from the placebo group only. First, a monotone missingness pattern will be enforced using Markov Chain Monte Carlo (MCMC). The MCMC process will use predictor variables of:

- baseline abscess count (continuous)
- baseline inflammatory nodule count (continuous)
- baseline draining fistula count (continuous)
- age (continuous)
- baseline BMI (continuous)

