A stratified test of response rates will be used for the primary analysis. Within each of the 4 strata used for randomization, the response rate for each treatment group and corresponding standard error will be calculated. The difference in response rates (risk difference) will be calculated for each stratum. The common risk difference among the 4 strata and associated standard error will be estimated by combining the observed risk differences using Cochran-Mantel-Haenszel weighting. The estimated risk difference divided by the standard error will be used as the test statistic and a p-value calculated assuming that the test statistic follows a standard normal distribution under the null hypothesis. Analyses at earlier timepoints when data to calculate the HiSCR75 are collected will also be presented using the same methodology. P-values from earlier timepoints and Week 16 will be presented for descriptive purposes, not part of the alpha-preserving multiple testing strategy.

Sample SAS code with stratification factors of comparing each dosing regimen of izokibep to the combined placebo group is given as following:

```
ods output commonpdiff = ;
proc freq data= ;
  tables stratum * treatment * response / cmh commonriskdiff (test=mh cl=mh);
  weight count / zeros;
run;
```

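### Three minor SAP inconsistencies in descriptive outputs: Table 3 discontinuation rows that do not nest, Week 52 compliance not reconciled with early termination, and a mislabelled, inconsistent HiSCR list in Section 5

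*SAP*

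**What the plan says.** **Disposition.** SAP Section 6.3, Table 3, has two study rows that should be part and whole.

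- The *within Period 2* row needs the End of Study form marked not completed and at least one Period 2 visit. It has no Week 52 condition.
- The *any time before Week 52* row needs the same form entry, a missing Week 52 analysis visit (windowed visits count as present), and no results at visits after Week 16.
- A separate *Discontinued Study* row rests on the form entry alone.

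In SAP Section 6.2.2 the Week 52 window opens at Day 295 and has no upper end.

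**Compliance.** SAP Section 6.10.1 measures doses taken against doses due over the planned treatment duration. It fixes the expected number at 16 by Week 16, 52 by Week 52 and 36 for Period 2, with categories split at 80%. SAP Sections 2 and 4.1 say that the study ends early, after all subjects have completed or discontinued treatment at Week 32, and that the analyses reflect this.

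**HiSCR list.** SAP Section 5 opens its list with "The efficacy endpoints for which analyses will be done as-written will be limited to the following", places "HiSCR75 at Week 16" under a primary heading and closes the list with "All remaining exploratory efficacy endpoint analyses will not be performed". SAP Section 9.5 states "The primary efficacy variable is defined as HiSCR75 at Week 12", and on other weeks "P-values from earlier timepoints and Week 16 will be presented for descriptive purposes, not part of the alpha-preserving multiple testing strategy". Section 5 gives Weeks 2, 4, 8, 16 and 32 for HiSCR50, 90 and 100. Section 6.9 gives those five weeks for all four levels. Section 9.7 gives all four levels at Weeks 2, 4, 8, 16, 24 and 32.

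**The concern.** A discontinuation count at any time before Week 52 should contain the Period 2 count. As defined, a subject who leaves in Period 2 with any later result enters the part and is barred from the whole. The disposition table can therefore show more people leaving in Period 2 than leaving at all.

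The compliance category can record a sponsor decision as poor adherence.

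Section 5 is the SAP's own record of departures from the protocol. There, a wrong primary label and a list that conflicts with the analysis sections leave a programmer unsure which HiSCR outputs to produce.

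**Working it through.** **1. Table 3 rows**

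Both rows need the form marked not completed. The other conditions give:

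| Subject | Within Period 2 | Any time before Week 52 |
|---|---|---|
| Leaves in Period 1, no later result | no | yes |
| Leaves in Period 2 with a result after Week 16, no Week 52 visit | yes | no |
| Early termination visit on or after Day 295, windowed to Week 52 | yes | no |
| Attends Week 52, does not complete the study (for example, misses Week 59) | yes | no |

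The rows hardly overlap, and the last subject is wrongly counted as leaving before Week 52. The matching treatment-disposition rows do nest, which points to a drafting slip.

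Illustration (assumed numbers): 2 subjects leave in Period 1 and 20 in Period 2, and 3 of the 20 have an early termination visit on or after Day 295.

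- As written: any time = 2, within Period 2 = 20.
- Change only the any-time row to refer to Week 52: 2 + (20 − 3) = 19 against 20, still not nested.
- Add the windowed Week 52 condition to both rows: 19 and 17. They nest, but 3 real discontinuers are lost.
- Use an actual Week 52 visit in both rows: 2 + 20 = 22 and 20. They nest and nobody is lost.

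Worst case (assumed): 80% to 95% of the 250 planned subjects reach Period 2 and have a result after Week 16, the rest leave earlier, and all are stopped before Day 295 and recorded as not completed. The Period 2 row then shows 200 to about 238 and the any-time row 50 to about 12. The *Discontinued Study* row shows 250.

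**2. Compliance**

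The SAP's figures reproduce from weekly dosing: Weeks 0–15 = 16, Weeks 0–51 = 52, Weeks 16–51 = 36.

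For a subject with no missed dose who is stopped at Week 32:

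- last dose at Week 31: 32/52 = 61.5% in total; 16/36 = 44.4% in Period 2
- last dose at Week 32: 33/52 = 63.5% in total; 17/36 = 47.2% in Period 2

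Reaching 80% takes 42 of 52 doses (41/52 = 78.8% fails), so dosing to Week 41. In Period 2 it takes 29 of 36 (28/36 = 77.8% fails), so dosing to Week 44. A subject stopped at Week 32 is therefore always below 80%.

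With expected doses cut off after Week 31 (assumed), the same subject scores 32/32 and 16/16 = 100%. A subject who quits for another reason after 20 doses scores 20/32 = 62.5% (20/52 = 38.5% as written) and stays below 80%.

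**3. HiSCR lists, counted as level by week**

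- Section 5: 1 + 3 × 5 = 16
- Section 6.9: 4 × 5 = 20
- Section 9.7: 4 × 6 = 24

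Sections 5 and 9.7 differ on 24 − 16 = 8: HiSCR75 at Weeks 2, 4, 8, 24 and 32, and the other three levels at Week 24. Section 9.5 covers HiSCR75 before Week 12: "Analyses at earlier timepoints when data to calculate the HiSCR75 are collected will also be presented using the same methodology". Crediting Weeks 2, 4 and 8 leaves 24 − 19 = 5: HiSCR75 at Week 32, and Week 24 for four levels. Sections 6.9 and 9.7 also differ from each other on 24 − 20 = 4, all at Week 24.

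**The case against.** **Disposition.** The *Discontinued Study* row, with its reasons, gives the correct overall total in the same table. That stands: a reader who inferred that the total is lost would be wrong. It does not repair the two rows. Nor is the Period 2 row sound as it is, because it counts a subject who attended Week 52.

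**Compliance.** The 52 and 36 follow exactly from the planned-duration definition and are right for anyone scheduled to Week 51, so they are not arithmetic errors. Dose counts, treatment duration and discontinuation reasons are tabulated separately, so the cause of a low value can be traced. The termination wording also does not rule out that early enrollees were dosed beyond Week 32. All of this stands. What remains is that the category was not reconciled with a termination that the same SAP announces.

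**HiSCR list.** If Section 9.7 governs, nothing is unresolved; set directly against Section 5, the difference is 8. The count of 5 depends on crediting Section 9.5. Support for Week 24 is also mixed: the protocol's endpoint column has it for all four levels, its objectives column only for HiSCR75, and SAP Section 3.3 for none. This stands as a caution on the count. It does not reconcile the lists with Section 5's closing sentence.

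**The tempting stronger reading** is that Section 5 moves the primary timepoint to Week 16 or drops the Week 12 test. The documents do not support it. SAP Sections 3.1, 6.7, 8.6 and 9.5 all keep Week 12. On scope, Section 4.1 says "This document defines the final analysis", and Section 8.6 speaks of the Week 12 analysis as past: "At the time of the primary analysis of Week 12 data, some data was available for subjects at Week 16, but not all". Section 5 omits Week 12 for every endpoint, so it seems to cover only the other timepoints, without saying so.

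**Conclusion.** All three inconsistencies are real, and the severity is minor. The Table 3 any-time row is wrong as written, and the Period 2 row lacks a condition. The compliance rule is consistent with its definition but misleading for subjects whom the sponsor stopped. The Section 5 label is wrong, and its HiSCR weeks do not match Sections 6.9 and 9.7.

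Only descriptive outputs are affected. Week 16 compliance is unaffected, and SAP Section 8.1 treats summaries after Week 16 as exploratory.

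The number of subjects misclassified cannot be given, because the documents do not say how far each was dosed or followed. The Table 3 counts above are illustrations under stated assumptions, and subjects who finished Week 52 before termination would reduce them.

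**What to change.** - **Table 3.** In the any-time row, refer to results after Week 52 instead of Week 16. Put one identical Week 52 condition in both rows, based on an actual Week 52 visit and not on an early termination visit windowed to it. An early leaver's safety follow-up visit should not count as a result after Week 52. The *Completed Study at Week 52* row still accepts windowed visits, so align it or footnote the overlap.
- **Section 6.10.1.** For every subject, whatever the reason for stopping, count as expected only the doses scheduled up to the earlier of Week 51 and the sponsor's termination cut-off, and state that cut-off. Subjects who stop for other reasons are still charged for doses missed before it.
- **Sections 5, 6.9 and 9.7.** Relabel HiSCR75 at Week 16 as exploratory, state that the Week 12 primary and secondary analyses are unchanged, and use one HiSCR week list in all three sections.

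The cost is SAP text, one denominator rule and the disposition definitions, with no new data.
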